4.4 Replacement of subjects

Should a patient withdraw or not be able to complete therapy with durvalumab and tremelimumab and study biopsy, additional subjects can be enrolled at the discretion of [name] and/or [name] to complete the 15 patient accrual with scheduled biopsies.

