Durvalumab, 1500 mg Q4W (equivalent to 20 mg/kg Q4W) for 2 doses/cycles in patients ≥ 30 kg
Tremelimumab 75 mg Q4W (equivalent to 1 mg/kg Q4W) for 2 doses/cycles in patients ≥ 30 kg
Weight-based dosing should be utilized for patients <30 kg durvalumab 20 mg/kg Q4 and tremelimumab 1 mg/kg Q4

Study Assessments and Criteria for Evaluation:

The study's primary endpoints are to evaluate the feasibility of enrolling patients with HR+/HER2- breast cancer onto a trial evaluating investigational agents prior to initiating standard neoadjuvant chemotherapy and to evaluate the safety and tolerability of tremelimumab plus durvalumab in patients with HR+/HER2- breast cancer.

Feasibility Assessments:

Feasibility will be measured by 2 achievements. If both are met, then upfront treatment with tremelimumab plus durvalumab will be feasible for future trials in HR+/HER2- breast cancer patients. The 2 measures are:

- Patients are willing to enroll. This will be established if we can enroll all 15 patients within 12 months of starting the study.
- Patients can complete the protocol. If at least 10 patients complete the study and have available immune data, the trial meets this feasibility criterion.

Safety Assessments:

All patients who receive at least one dose of study drug will be included in the safety monitoring and safety analysis. For trial monitoring and decisions about future trials, a patient will be determined to have an extreme toxicity (ETOX) if either condition is met:

- The patient experiences any grade 3 or higher adverse event (AE) that is possibly, probably, or definitely related to therapy received on this protocol and occurs up to 90 days after the last dose of therapy (durvalumab + tremelimumab). As an exception, any such AE that is potentially treatable with steroids will only count as an ETOX if it does not improve to grade 1 or better within 2 weeks.
- The patient has a delay in surgery of 6 weeks or more due to AE, even if that AE does not meet the definition of ETOX

Statistical Methods and Data Analysis:

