6. TREATMENT PLAN

6.1 Subject enrollment

Patients who have signed informed consent and have undergone screening will be enrolled onto this study and can begin therapy. There is no randomization. This is a single arm, open-label presurgical pilot study prior to the initiation of standard neoadjuvant chemotherapy of the physician's choice for patients with clinical stage II-III HR+/HER2- breast cancer. Patients who are unable to complete all

scheduled study requirements including the pre and post treatment breast biopsies can be replaced at the request of [name] and/or [name] and/or the study team.

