6.1.1 Procedures for handling subjects incorrectly enrolled

Subjects who are incorrectly enrolled, but not yet initiated on treatment will be withdrawn from the study and replaced.

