8.1.3 End of Treatment

End of treatment is defined as the last planned dose of tremelimumab and durvalumab. This will be followed by physician's choice of systemic therapy, followed by standard of care surgical intervention. Any further adjuvant therapy is at the discretion of the treating physician. Also, should the treating physician deem it is in the patient's best interest to proceed with surgery after the completion of the 2 doses each of tremelimumab and durvalumab, the physician may proceed with surgery with adjuvant therapies as per physician discretion.

All subjects will be followed until the time of breast surgery.

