11.1.2 Efficacy analysis set

All enrolled patients will be included in the primary feasibility analysis. Only patients with surgical specimens and immune measures will be included in secondary and exploratory analyses requiring that information.

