11.3 Endpoints

11.3.1 Primary Endpoints

The primary endpoints will be

:

1. Feasibility. This will be measured by 2 achievements. If both are met, then upfront treatment with durvalumab plus tremelimumab will be feasible for future trials in these breast cancer patients. Otherwise, other strategies for implementing these treatments will need to be designed. The 2 measures are:
 - a. Patients are willing to enroll: This will be established if we can enroll all 15 patients within 12 months of starting the study. The start date for measuring feasibility will be the date the first patient is screened.
 - b. Patients can complete the protocol: If at least 10 patients complete the study and have available immune data the trial meets this feasibility criterion. If fewer than 8 finish then this dose/schedule is infeasible. If 8 or 9 complete the study with immune data then clinical judgment combining toxicity, efficacy, and physician

experience with the protocol will be used to determine whether adjustments to the treatment are needed before a future trial.

2. Adverse events will be recorded according to CTCAE 4.03.

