11.4 Sample Size Considerations

The selection of 15 patients for this pilot trial is to provide preliminary information for feasibility and safety, as well as to have at least 10 patients with full immune measures pre and post treatment for hypothesis generation and testing in the next trial. An accrual rate of 2 patients per month is anticipated. A maximum sample size of 15 patients will be enrolled. No hypotheses will be formally tested, but with 15 patients we can determine whether an unreasonable proportion of patients have high grade toxicities and gather estimates of immune and molecular changes in tumor and peripheral blood. These measures will be used to design a larger, hypothesis-driven trial.

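### Uncapped replacement (4.4, 6.1) conflicts with the maximum of 15 enrolled (11.4, synopsis), and feasibility criterion (b) is a count with no denominator

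*Combined protocol and SAP*

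**What the plan says.** **Replacement.** Section 4.4 applies to patients who withdraw or cannot complete therapy and the study biopsy; more patients may be added at discretion "to complete the 15 patient accrual with scheduled biopsies". Section 6.1 has a wider trigger: patients who cannot complete all "scheduled study requirements including the pre and post treatment breast biopsies can be replaced at the request of" the named investigators or the study team. Only 4.4 states a target of 15 with biopsies. Section 6.1.1 deals with a separate group: "Subjects who are incorrectly enrolled, but not yet initiated on treatment will be withdrawn from the study and replaced". None of the three gives an upper limit on total enrolment.

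**Sample size.** Section 11.4 and the synopsis state "A maximum sample size of 15 patients will be enrolled". The Table 1 footnote (3.3 and 11.5) also ends the trial at 15 patients.

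**Criterion (b).** Section 11.3.1 states "If at least 10 patients complete the study and have available immune data the trial meets this feasibility criterion". Fewer than 8 is infeasible, and 8 or 9 goes to clinical judgment. The synopsis gives only the pass mark of 10. Neither place gives a denominator or mentions replacement.

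**Analysis set and reporting.** Section 11.1.2 states "All enrolled patients will be included in the primary feasibility analysis". Section 11.6 reports the number screened to reach 15 enrolled, but not the number enrolled in total or replaced.

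**The concern.** Criterion (b) is meant to show that patients can complete the protocol. Together with criterion (a), 15 enrolled within 12 months, it decides whether upfront treatment is called feasible for future trials. Under 4.4 and 6.1, the event that permits an extra patient is the kind of failure that (b) is meant to detect. If enrolment can pass 15 in this way, each failure may buy another chance of a completer while costing nothing in the count. The same true completion rate could then pass or fail according to how many patients were added at discretion. If enrolment cannot pass 15, the 4.4 target is out of reach as soon as one enrolled patient fails to complete. The two sets of passages cannot both be followed in full.

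**Working it through.** **1. The plan's own figures.** No calculation is given for criterion (b) or for the choice of 15. The toxicity tables can be checked. With the beta(0.2, 0.8) prior, the posterior after r ETOX in n patients is beta(0.2 + r, 0.8 + n − r). The probability that the rate exceeds 0.20 is 0.9275 at 3/6, 0.9044 at 4/10 and 0.9203 at 5/13. It falls below 0.90 with one more patient in each case (0.8861, 0.8692, 0.8935), so the first three Table 1 limits reproduce. An exact recursion with looks from patient 5 to 14 and a maximum of 15 gives early-stopping probabilities of 0.0028, 0.0239, 0.1743, 0.4492 and 0.7244. Table 2 states 0.003, 0.02, 0.17, 0.45 and 0.72. The monitoring design was therefore computed for a maximum of 15.

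**2. What 10 completers means.** 10/15 = 67%; 10/20 = 50%; 10/24 = 42%.

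**3. Chance of meeting (b).** Let q be the probability that an enrolled patient completes with immune data, and M the total to which enrolment may run. Both are assumptions. If patients are replaced until there are 15 completers or M is reached, the criterion is met exactly when a Binomial(M, q) count is at least 10, so P = Σ C(M, k) q^k (1 − q)^(M − k) for k = 10 to M.

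| q | M = 15 | M = 17 | M = 20 |
|---|---|---|---|
| 0.5 | 0.15 | 0.31 | 0.59 |
| 0.6 | 0.40 | 0.64 | 0.87 |
| 0.7 | 0.72 | 0.90 | 0.98 |
| 0.8 | 0.94 | 0.99 | 1.00 |

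The infeasible verdict moves too: at q = 0.5 the chance of fewer than 8 completers is 0.50 with M = 15 and 0.13 with M = 20. These figures ignore toxicity stopping. I give no adjusted version, because it would need an assumed link between toxicity and completion, and 4.3 makes adverse events a ground for discontinuation.

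**4. Whether the calendar limits this.** At the planned 2 patients per month, 15 take 15/2 = 7.5 months, and 24 fit into 12 months. If criterion (a) counts every enrolled patient, it does not restrain replacement. If it counts only patients with biopsies, let p be the assumed probability of completing therapy and biopsy; the mean total needed is 15/p. At p = 0.6 that is 25.0 patients, or 12.5 months, so (a) would typically fail. At p = 0.7 it is 21.4 patients, or 10.7 months, so (a) would typically hold.

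**5. Toxicity tables, only if more than 15 are treated.** The posterior for 6 ETOX is 0.9513 at 15, 0.9126 at 17 and 0.8884 at 18. The fixed verdict at 6 ETOX and the 90% rule agree through 17 treated and part at 18.

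**The case against.** The best answer is that 15 is a firm cap. Besides 11.4 and the synopsis, section 1.3 says each platform trial needs only 15, section 3.1 says 15 will be enrolled, the Table 1 footnote stops there, and 11.6 refers to 15 enrolled patients. Replacement is permissive, so (b) may simply be 10/15. This stands as a likely reading, and under it there is no inflation. It does not settle the matter, because 4.4 and 6.1 are current text and permit the opposite.

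A reader might also infer that replaced patients have no status in the analysis. The documents do not support that: 11.1.2 keeps all enrolled patients in the feasibility analysis, and 11.1.1 keeps every dosed patient in the safety set. The gap is narrower. Being in the set has no effect on a count without a denominator.

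Two further points stand in part. Section 11.4 gives a reason for a count, namely at least 10 patients with full immune measures; that justifies replacement for the immune data, not for judging completion. And this is a pilot with no formal test, in which 8 or 9 completers already goes to judgment; but 10 or more, and fewer than 8, are still fixed verdicts. The numbers replaced could probably be traced through 4.3 and the monthly summaries in 11.5, but 11.6 does not list them.

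**Conclusion.** The conflict between the replacement rules and the maximum of 15 is real, and it reaches half of the feasibility primary endpoint through the missing denominator. It should be fixed, though it is not shown that the result will be inflated. The size depends on two things the documents do not give, a completion rate and a total above 15. At an assumed q of 0.6, five extra patients raise the chance of passing from 0.40 to 0.87; at q = 0.8 it goes from 0.94 to 1.00, which matters little. With the cap enforced the effect is nil. A 12-month limit that counts only patients with biopsies would give partial protection at low completion. It would be too strong to say that both replacement sections set the 15-with-biopsies target, or that the plan as a whole intends to exceed 15.

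**What to change.** - **4.4, 6.1, 11.4 and synopsis:** state whether 15 counts enrolled patients or patients with biopsies, and give the maximum total enrolment including replacements. Use one replacement trigger. If nothing above 15 is intended, say so in 4.4 and 6.1; criterion (b) then stands at 10/15.
- **11.3.1 and synopsis:** judge (b) on the first 15 enrolled, counting anyone replaced under 4.4 or 6.1 as a non-completer, with the cut-offs (10 or more, 8–9, fewer than 8) unchanged. Say whether untreated patients replaced under 6.1.1 are among the 15.
- **11.1.2:** align it, so that replacements contribute to the immune and safety analyses only.
- **11.6:** report the numbers enrolled and replaced, with reasons.
- **Only if more than 15 may be treated:** extend Tables 1 and 2 to the new maximum, and reconcile the fixed 6-ETOX verdict with the 90% rule from 18 treated onward.

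The cost is protocol and SAP wording, with recalculation only in the last case. The downside is that the feasibility result may look less favourable.

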5. INVESTIGATIONAL PRODUCT(S)

5.1 Durvalumab and tremelimumab

The Investigational Products Supply section of AstraZeneca/MedImmune will supply durvalumab and tremelimumab to the investigator as a solution for infusion after dilution.

5.1.1 Formulation/packaging/storage

Durvalumab

Durvalumab will be supplied by AstraZeneca as a 500-mg vial solution for infusion after dilution. The solution contains 50 mg/mL durvalumab, 26 mM histidine/histidine-hydrochloride, 275 mM trehalose dihydrate, and 0.02% (weight/volume) polysorbate 80; it has a pH of 6.0. The nominal fill volume is 10 mL. Investigational product vials are stored at 2°C to 8°C (36°F to 46°F) and must not be frozen. Durvalumab must be used within the individually assigned expiry date on the label.

Tremelimumab

Tremelimumab will be supplied by AstraZeneca as a 400-mg vial solution for infusion after dilution. The solution contains 20 mg/mL of tremelimumab, 20 mM histidine/histidine hydrochloride, 222 mM trehalose dihydrate, 0.02% (w/v) polysorbate 80, and 0.27 mM disodium edetate dihydrate (EDTA); it has a pH of 5.5. The nominal fill volume is 20 mL. Investigational product vials are stored at 2°C to 8°C (36°F to 46°F) and must not be frozen. Tremelimumab must be used within the individually assigned expiry date on the label.

5.2 Dose and treatment regimens

5.2.1 Treatment regimens

Durvalumab + tremelimumab combination therapy

Patients will receive 1500 mg durvalumab via IV infusion q4w \pm 3 days for 2 doses/cycles and 75 mg tremelimumab via IV infusion q4w \pm 3 days for 2 doses/cycles. Dosing outside the window should be discussed with [name] and/or [name]. Tremelimumab will be administered first. Durvalumab infusion will start approximately 1 hour after the end of tremelimumab infusion. The duration will be approximately 1 hour for each infusion. A 1-hour observation period is required after the first infusion of durvalumab and tremelimumab. If no clinically significant infusion reactions are observed during or after the first cycle, subsequent infusion observation periods will be 30 minutes \pm 5 minutes unless otherwise specified by the investigator.

5.2.2 Duration of treatment

Patients will receive 1500 mg durvalumab via IV infusion q4w \pm 3 days for 2 doses/cycles and 75 mg tremelimumab via IV infusion q4w \pm 3 days for up to 2 doses/cycles. A standard regimen of neoadjuvant chemotherapy will be initiated within 28 days after the last infusion of durvalumab and tremelimumab. A biopsy will be obtained after the last infusion of durvalumab and tremelimumab before chemotherapy is started.

5.2.3 Study drug preparation of durvalumab and tremelimumab

Based on average body WT of 75 kg, a fixed dose of 1500 mg Q4W durvalumab (equivalent to 20 mg/kg Q4W) and 75 mg Q4W tremelimumab (equivalent to 1 mg/kg Q4W) is included in the current study.

Preparation of durvalumab doses for administration with an IV bag

The dose of durvalumab for administration must be prepared using aseptic technique. Total time from needle puncture of the durvalumab vial to the start of administration should not exceed:

- 24 hours at 2°C to 8°C (36°F to 46°F)
- 4 hours at room temperature

If in-use storage time exceeds these limits, a new dose must be prepared from new vials. Infusion solutions must be allowed to equilibrate to room temperature prior to commencement of administration.

No incompatibilities between durvalumab and polyvinylchloride or polyolefin IV bags have been observed. Dose of 1500mg durvalumab for patients \geq 30 kg will be administered using an IV bag containing 0.9% (w/v) saline, with a final durvalumab concentration ranging from 1 to 20 mg/mL, and delivered through an IV administration set with a 0.2- or 0.22- μ m in-line filter. Remove 30.0 mL of IV solution from the IV bag prior to addition of durvalumab. Next, 30.0 mL of durvalumab (ie, 1500 mg of durvalumab) is added to the IV bag such that final concentration is within 1 to 20 mg/mL (IV bag volumes 100 to 1000 mL). Mix the bag by gently inverting to ensure homogeneity of the dose in the bag.

Patient weight at baseline should be used for dosing calculations unless there is a $\geq 10\%$ change in weight. Dosing day weight can be used for dosing calculations instead of baseline weight per institutional standard.

For patients $< 30\text{kg}$, Calculate the dose volume of durvalumab and tremelimumab and number of vials needed for the subject to achieve the accurate dose.

Durvalumab will be administered at room temperature (approximately 25°C) by controlled infusion via an infusion pump into a peripheral or central vein. Following preparation of durvalumab, the entire contents of the IV bag should be administered as an IV infusion over approximately 60 minutes (± 5 minutes), using a 0.2, or 0.22- μm in-line filter. Less than 55 minutes is considered a deviation.

The IV line will be flushed with a volume of IV solution (0.9% [w/v] saline equal to the priming volume of the infusion set used after the contents of the IV bag are fully administered, or complete the infusion according to institutional policy to ensure the full dose is administered and document if the line was not flushed.

Standard infusion time is 1 hour. However, if there are interruptions during infusion, the total allowed time should not exceed 8 hours at room temperature. The table below summarizes time allowances and temperatures.

Durvalumab hold and infusion times

Maximum time from needle puncture to start of administration	4 hours at room temperature, 24 hours at 2°C to 8°C
Maximum time for IV bag infusion, including interruptions	8 hours at room temperature

In the event that either preparation time or infusion time exceeds the time limits outlined in the table, a new dose must be prepared from new vials. Durvalumab does not contain preservatives, and any unused portion must be discarded.

Preparation of tremelimumab doses for administration with an IV bag

The dose of tremelimumab for administration must be prepared using aseptic technique. Total time from needle puncture of the tremelimumab vial to the start of administration should not exceed:

- 24 hours at 2°C to 8°C (36°F to 46°F)
- 4 hours at room temperature

It is recommended that the prepared final IV bag be stored in the dark at 2°C - 8°C (36°F - 46°F) until needed. If storage time exceeds these limits, a new dose must be prepared from new vials. The

refrigerated infusion solutions in the prepared final IV bag should be equilibrated at room temperature for about 2 hours prior to administration. Tremelimumab does not contain preservatives and any unused portion must be discarded.

No incompatibilities between tremelimumab and polyvinylchloride or polyolefin IV bags have been observed. Doses of 75 mg tremelimumab for patients ≥ 30 kg will be administered using an IV bag containing 0.9% (w/v) saline, with a final tremelimumab concentration ranging from 0.1 mg/mL to 10 mg/mL, and delivered through an IV administration set with a 0.2 μm or 0.22 μm in-line filter. Remove 3.8 mL of IV solution from the IV bag prior to addition of tremelimumab. Next, 3.8 mL of tremelimumab (ie, 75 mg of tremelimumab) is added to the IV bag such that final concentration is within 0.1 mg/mL to 10 mg/mL (IV bag volumes 50 to 500 mL). Mix the bag by gently inverting to ensure homogeneity of the dose in the bag.

Patient weight at baseline should be used for dosing calculations unless there is a $\geq 10\%$ change in weight. Dosing day weight can be used for dosing calculations instead of baseline weight per institutional standard.

For patients < 30 kg, Calculate the dose volume for tremelimumab and number of vials needed for subject to achieve the accurate dose.

Tremelimumab will be administered at room temperature (approximately 25°C) by controlled infusion via an infusion pump into a peripheral or central vein. Following preparation of tremelimumab, the entire contents of the IV bag should be administered as an IV infusion over approximately 60 minutes (± 5 minutes), using a 0.2, or 0.22- μm in-line filter. Less than 55 minutes is considered a deviation.

The IV line will be flushed with a volume of 0.9% (w/v) saline equal to the priming volume of the infusion set used after the contents of the IV bag are fully administered, or complete the infusion according to institutional policy to ensure the full dose is administered and document if the line was not flushed.

Standard infusion time is 1 hour. However, if there are interruptions during infusion, the total allowed time should not exceed 8 hours at room temperature. The table below summarizes time allowances and temperatures.

Tremelimumab hold and infusion times

Maximum time from needle puncture to start of administration	4 hours at room temperature, 24 hours at 2°C to 8°C
Maximum time for IV bag infusion, including interruptions	8 hours at room temperature

In the event that either preparation time or infusion time exceeds the time limits outlined in the table, a new dose must be prepared from new vials. Tremelimumab does not contain preservatives, and any unused portion must be discarded.

5.2.4 Monitoring of dose administration

Patients will be monitored during and after the infusion with assessment of vital signs as per Schedule of Study Assessments.

A 1-hour observation period is required after the first infusion of durvalumab and tremelimumab.

In the event of a \leq Grade 2 infusion-related reaction, the infusion rate of study drug may be decreased by 50% or interrupted until resolution of the event and re-initiated at 50% of the initial rate until completion of the infusion. For patients with a \leq Grade 2 infusion-related reaction, subsequent infusions may be administered at 50% of the initial rate. Acetaminophen and/or an antihistamine (eg, diphenhydramine) or equivalent medications per institutional standard may be administered at the discretion of the investigator. If the infusion-related reaction is \geq Grade 3 or higher in severity, study drug will be discontinued.

As with any antibody, allergic reactions to dose administration are possible. Appropriate drugs and medical equipment to treat acute anaphylactic reactions must be immediately available, and study personnel must be trained to recognize and treat anaphylaxis. The study site must have immediate access to emergency resuscitation teams and equipment in addition to the ability to admit patients to an intensive care unit if necessary.

